5.1.1. CAM2038 q1w (Once Weekly)

Subcutaneous CAM2038 q1w has so far been investigated after single and repeated doses in 3 clinical trials, in both patients and healthy volunteers. An initial study assessed pharmacokinetics, pharmacodynamics and safety in opioid dependent patients (Study HS-07-307). Study HS-07-307 results also showed that CAM2038 q1w was well tolerated, both locally and systemically. Importantly, no treatment emergent serious adverse events (SAEs) were observed and drug-related local tolerability findings were limited to 4 of 42 patients (9.5%). Three patients experienced mild injection site pain and 1 patient exhibited transient injection site inflammation (mild) and injection site pruritus (moderate). Two additional clinical studies were subsequently performed in healthy volunteers (under naltrexone blockade) to assess the

pharmacokinetics and bioavailability of single and repeat doses of CAM2038 q1w versus repeated doses of sublingual (SL) BPN (i.e., at steady state) and single dose of intravenous (IV) BPN (Studies HS-11-426 and HS-13-487). These two studies demonstrated that after administration of the studied doses of CAM2038 q1w, the plasma concentrations corresponded to those obtained after administration of SL BPN at approved doses. The BPN levels after administration of CAM2038 q1w were furthermore similar in healthy volunteers and patients with opioid dependence. The systemic tolerability of CAM2038 q1w was good in both studies and similar to the reference IV and SL BPN products. Local tolerability in Study HS-11-426 ($N_{\text{safety}}=60$) was very good with no adverse events (AEs) attributed to injection site tolerability. Similarly, local tolerability of CAM2038 q1w was very good in Study HS-13-487, featuring 4 repeated SC injections of CAM2038 q1w into the buttock site (1 subject reported 1 AE of injection site pain).

Based on these studies, the following main conclusions were drawn regarding clinical properties of CAM2038 q1w:

- Extended BPN release over one week at target plasma concentrations
- Dose proportionality and flexible/multiple dosing options
- 6- to 8-fold higher bioavailability versus SL BPN
- BPN plasma concentrations over 7 days within ranges of those produced by corresponding SL BPN doses at steady-state (i.e., approved 8 mg, 16 mg, or 24 mg doses), supporting dose selection for this Phase III study
- Observed and predicted (repeated dose), C_{average} and C_{trough} values for CAM2038 q1w within therapeutic plasma levels
- Repeated-dose administration demonstrated time-independent pharmacokinetics
- Good safety and systemic tolerability in patients
- Safety in healthy volunteers comparable to reference IV and SL BPN treatments
- Good local tolerability in patients and healthy volunteers

The clinical pharmacokinetic profile and good systemic and local tolerability of CAM2038 q1w evidenced in subjects in these 3 studies is also supported by a large body of data generated in non-clinical pharmacokinetic and toxicology studies in the dog, minipig and rat of single and repeat SC doses of CAM2038 q1w, including repeat weekly doses of the FC vehicle formulation for 6-months. In summary, nonclinical data have indicated no systemic toxicity associated with CAM2038 q1w or the FC injection depot vehicle. Subcutaneous administration of CAM2038 q1w has been shown to be well tolerated both systemically and locally in single and repeat dose non-clinical studies in the rat and in the dog. The treatment-related findings have been limited to clinical observations in agreement with and considered related to known pharmacological effects of the drug substance BPN, and to reversible, local inflammatory reactions at the SC site of injection. The latter findings were similar to the physiological response to a foreign body. The FC related injection site findings appeared to be reversible and self-limiting, and only apparent at the immediate vicinity of test article deposition.

5.1.2. CAM2038 q4w (Once Monthly)

Subcutaneous CAM2038 q4w has been investigated after single administration in the bridging clinical pharmacokinetic study in healthy volunteers versus repeated dose CAM2038 q1w (i.e., at steady state), repeated dose SL BPN (i.e., at steady state), and single dose of intravenous (IV)

BPN (Study HS-13-487). The following conclusions can be drawn regarding the clinical properties of CAM2038 q4w:

- Extended BPN release over 4 weeks at target plasma concentrations
- Dose proportionality was shown within the dosage interval of 64 to 192 mg CAM2038 q4w
- 6- to 8-fold higher bioavailability than SL BPN, comparable to CAM2038 q1w
- Observed BPN plasma concentrations over 4 weeks comparable to CAM2038 q1w over one week, and to SL BPN over 24 hours at steady-state (i.e., for approved 8 mg, 16 mg, or 24 mg doses), supporting dose selection for this Phase III study
- Predicted $C_{ss,av}$ and $C_{ss,trough}$ values for 64, 96 and 128 mg CAM2038 q4w similar to CAM2038 q1w and SL BPN (i.e., for approved 8 mg, 16 mg, or 24 mg doses)
- Safety profile comparable to reference IV and SL BPN treatments
- Good local tolerability

The most commonly reported drug-related AEs after CAM2038 q1w and CAM2038 q4w administration to the healthy volunteers under naltrexone blockade in the study were nausea (63% of subjects), dizziness (54% of subjects) and vomiting (39% of subjects). The local tolerability was good with 6 subjects experiencing 7 AEs that were assessed as related to CAM2038 q4w (injection site reactions, injection site pain, injection site induration and application site bruise). Two SAEs were reported by 2 subjects after treatment with 192 mg CAM2038 q4w. The first SAE was an event of withdrawal reaction and the second SAE was an event of dehydration due to nausea and vomiting. Both SAEs were assessed as related to CAM2038 q4w (withdrawal reaction was also assessed as related to the concomitant treatment with naltrexone) and the event of withdrawal reaction qualified for reporting as a suspected unexpected serious adverse reaction (SUSAR). There were no deaths or any other significant AEs and most of the AEs were mild and transient. Analysis of clinical chemistry, hematology and urinalysis parameters did not suggest any significant safety issues for CAM2038 q4w.

The non-clinical assessment of CAM2038 q4w and the FC vehicle, supported by publically available data for the drug substance buprenorphine and for the components of the vehicle, suggests safe use of CAM2038 q4w for the proposed clinical development. This conclusion is further supported by results from non-clinical and clinical studies of the once weekly product, CAM2038 q1w, comprising the same active substance and functional lipid components.

Additional information about CAM2038 can be found in the current version of the Investigator's Brochure.

5.2. Study Rationale

Opioid drug dependence is a major health and social issue and is often a chronic medical condition that requires long-term maintenance treatment. An important aim of the treatment programs for opioid drug dependence is to enable the patients to become abstinent. Further important aims are to improve their mental and physical health, as well as their social conditions. This can be achieved by increasing patients' quality of life and reducing the burden on the society and relatives. Moreover, opioid people often inject with used syringes and needles, and

thus expose themselves to high risk of transmission of infectious diseases, including HIV and hepatitis C.

Opioid maintenance treatment, such as SL BPN, is one of the most effective treatment options available for opioid dependent drug users and is associated with substantial reductions in deaths, and HIV transmission (WHO, 2004). However, because patients often discontinue treatment prematurely, an outcome associated with higher rates of relapse to drug use, treatment strategies that aim to keep patients in treatment longer and/or improve patient adherence may have additional advantages (Chandler et al, 2009). While daily dosing with SL BPN has proven effective, the need for daily administration of treatment may negatively influence patients' compliance. Moreover, SL tablets or film can be easily diverted for illicit use, injected for greater effect, or accidentally ingested, especially by children (Chandler et al, 2009; Winstock et al, 2008). The limitations associated with SL BPN are of particular relevance to patients who have children at home, to those who have difficulty making frequent visits to the physician's office (e.g., patients in remote locations, those with limited mobility, or those who travel frequently) or to those who have difficulty managing the responsibility of daily dosing.

CAM2038 q1w and q4w may increase patient compliance relative to daily SL BPN dosage forms, and may help prevent treatment noncompliance in higher-risk patients (i.e., those patients who take "drug holidays" from their BPN when they wish to abuse illicit opioids). In addition, CAM2038 q1w and q4w may provide significant potential for reducing risks of diversion, abuse, and accidental pediatric exposure, which continue to be important public health consequences of SL BPN therapy.

In animal repeat-dose toxicity studies, CAM2038 q1w or FC vehicle formulation have been administered weekly for up to 6-months with no systemic toxicity associated with CAM2038 q1w or the FC injection depot vehicle observed. However, the long-term safety profiles of CAM2038 q1w and q4w in humans have not been described. In Study HS-13-487, pharmacokinetic profiles were evaluated for 4 repeat doses of CAM2038 q1w (one SC injection per week for 4 weeks) and one dose of CAM2038 q4w. In an upcoming parallel Phase III safety and efficacy study (HS-11-421), CAM2038 q1w and CAM2038 q4w will each be administered for up to 12 weeks (3 months). Therefore, the purpose of this study is to demonstrate the long-term safety of CAM2038 (q1w and q4w) as an office-based therapy for opioid maintenance treatment with BPN in patients with opioid use disorder.

5.3. Dosing Rationale

The weekly subcutaneous CAM2038 q1w product has so far been investigated after single and repeated doses in three separate clinical trials, in both patients and healthy volunteers. An initial study assessed pharmacokinetics, pharmacodynamics and safety in opioid dependent patients (Study HS-07-307). Following FDA's advice at the pre-IND meeting (PIND 114,082), two additional clinical studies were subsequently performed in healthy volunteers to assess the pharmacokinetics and bioavailability of CAM2038 q1w versus repeated doses of sublingual (SL) BPN (i.e., at steady state) and single dose of intravenous (IV) BPN (Studies HS-11-426 and HS-13-487). The total number of subjects exposed to CAM2038 q1w in these studies was 114.

Subcutaneous CAM2038 q4w has been investigated in one bridging clinical pharmacokinetic study in healthy volunteers versus repeat dose CAM2038 q1w, repeat dose SL BPN (i.e., at steady state), and single dose of intravenous (IV) BPN (Study HS-13-487). The total number of exposed subjects in this study was 79, with 62 subjects receiving CAM2038 q4w.

During the induction, stabilization, and as needed for maintenance treatments, subcutaneous doses of 8 to 32 mg CAM2038 q1w will be provided based on the clinical needs of the patients. This dose range is expected to cover the needs of patients that are currently eligible to SL BPN treatment. This assumption is based on the head-to-head comparison of BPN exposures of CAM2038 q1w versus SL BPN (Subutex®), which were assessed in the HS-11-426 and HS-13-487 Phase 1 trials. Occasionally, an SC booster injection of 8 mg CAM2038 q1w may be needed on top of the weekly dose of 32 mg. For maintenance treatment with CAM2038 q4w, the corresponding planned dose range is 64 mg to 160 mg.

Figures below demonstrate observed and predicted BPN plasma concentrations for different dose combinations of CAM2038 q1w, CAM2038 q4w and Subutex® over 28 days. These data demonstrate that observed and predicted plasma concentrations of CAM2038 q1w over one week and CAM2038 q4w over one month are comparable to SL BPN over 24 hours at steady-state (i.e., for approved 8 mg, 16 mg, or 24 mg doses), thus supporting doses selected for the Phase III studies.

Figures below are geometric mean observed steady state C_{max} and C_{trough} for Subutex from HS-11-426 and HS-13-487; Predicted plasma concentration versus time profiles for CAM2038 q1w from single and repeat dose data in HS-13-487; Observed steady state plasma concentration versus time profiles for CAM2038 q1w 16 mg from HS-13-487; and Predicted steady state plasma concentration versus time profiles for CAM2038 q4w from single-dose data in HS-13-487.

Figure 1: Observed and Predicted Plasma Concentration Versus Time Profiles for CAM2038

[figure not shown]

Figure 2: Predicted Plasma Concentration Versus Time Profiles For CAM2038

[figure not shown]
[figure not shown]

Figure 3: Predicted Plasma Concentration Versus Time Profiles For CAM2038

The following table demonstrates the estimation of plasma buprenorphine levels during the induction treatment with CAM2038 q1w. These plasma levels provide a rationale that induction treatment with CAM2038 q1w may mimic the gradual increase in the plasma buprenorphine levels provided with titration methods with SL BPN.

Table 1: Plasma Concentrations of Buprenorphine (Geometric Mean) After Single Subcutaneous Administration of CAM2038 q1w to Healthy Subjects Under Naltrexone Blockage

Time after dose (h)	Plasma concentrations of buprenorphine (ng/mL)		
	CAM2038 q1w 8 mg	CAM2038 q1w 16 mg	CAM2038 q1w 32 mg
Pre-dose	<0.025	<0.025	<0.025
0.5	0.0759	0.253	0.220
1	0.119	0.396	0.391
2	0.257	0.722	0.748
4	0.568	1.39	1.83
6	0.767	1.63	2.61
10	1.40	2.84	4.42

24	1.65	2.84	5.00
36	1.11	2.02	3.76

5.4. Overall Risk Benefit Assessment

BPN is a substance with well-established use in the treatment dependence on opioid drugs. The CAM2038 products contain BPN in a new FluidCrystal (FC) formulation for subcutaneous (SC) injection. Clinical trials have demonstrated effectiveness of BPN in reducing illicit opioid use and improving retention rates of patients in outpatient maintenance treatment of opioid dependence, as well as substantial reduction in criminal activity, deaths, and HIV transmission. The need for daily administration of SL BPN may negatively influence patients' compliance and BPN tablets or film can be easily diverted for illicit use, injected for greater effect, or accidentally ingested, especially by children.

CAM2038 q1w and CAM2038 q4w are ready-to-use, SC BPN FC Injection depots that are being developed as alternative dosage form for treatment of opioid drug dependence by providing extended BPN release at target plasma concentrations over the weekly and monthly dosing intervals, respectively. Due to the fact that CAM2038 products need to be administered by a clinician, CAM2038 products cannot be abused or diverted by patients. In addition, it may decrease the tendency for patients to request unnecessarily high BPN doses. It will also ensure that the dose required is the dose received. Compared with the sublingual buprenorphine products on the market, CAM2038 q1w and CAM2038 q4w have several potential advantages: 1) rapid therapeutic onset (with maximum plasma concentrations established within 24 hours after injection) followed by steady long-acting release; 2) reduced variation in buprenorphine plasma levels over time (stable plasma levels attained for at least 28 days (CAM2038 q4w) and 7 days (CAM2038 q1w) resulting in more consistent therapeutic plasma levels and a possible reduction in morning "cravings"; 3) less frequent dosing resulting in reduced frequency of clinic visits and need for medical support; 4) significantly higher bioavailability, meaning less drug substance in circulation and on the street; 5) decreased risk of drug diversion; and 6) easier dose adjustment.

To date, three Phase I/II clinical studies (HS-07-307, HS-11-426 and HS-13-487) have been conducted in both opioid dependent and healthy volunteers under naltrexone block. The safety profile of CAM2038 q1w and CAM2038 q4w is comparable to reference SL BPN approved treatment and good local tolerability was demonstrated with findings limited to only a few cases of transient, mild, local inflammation, pruritus and/or injection site pain.

A number of potential AEs can be associated with the administration of long-acting depots. The most severe side-effects specific for the investigational product that may occur are related to local reactions at the site of injection after subcutaneous administration and include dermal ulcers or necrotic wounds at the injection site. Additional potential AEs include over-dose of buprenorphine and allergy to buprenorphine. There is also a potential risk of local obstruction and blockage at the injection site with accidental intravascular injection

Systemic repeated toxicity for up to 4 months of once-weekly SC administration of CAM2038 q1w, once weekly and CAM2038 q4w, once-every-4-week administration in dogs showed absence of systemic toxicity by assessment of complete clinical pathology, histopathology and toxicokinetics (TK). The treatment related findings were limited to reversible clinical effects compatible with known pharmacological effects of BPN (reduced activity, ataxia, sporadic salivation, and intermittent soft faeces, as well as reduction in body weight and food consumption) and to local, transient injection site findings, characterised as foreign body response. No novel toxicological aspects arose for BPN in the CAM2038 drug product formulations in comparison with available information on the drug substance alone. Absence of systemic toxicity has also been shown for up to chronic SC exposure of the FC system in rodents and non-rodents. The local toxicity findings at the injection site following SC administration of the CAM2038 drug products in a large number of non-clinical studies were described by necropsies and histopathology as a reversible local continuum of an inflammatory response consistent with the physiological inflammatory reactions occurring in response to the injection of an insoluble material.

The current protocol is intended to demonstrate the long-term 12-month safety of CAM2038 q1w and q4w for the treatment of opioid dependence. The safety monitoring practices employed by this protocol are adequate to protect the patients' safety and should detect all expected treatment-emergent AEs (TEAEs).

The volume of blood removed from the subject is approximately 30 mL over the course of the entire study (Screening to Follow-up, but does not include repeat or additional tests ordered by the Investigator). This volume presents no undue risk to the subjects.

Therefore, CAM2038 q1w and q4w may provide alternative treatment options that potentially can increase patient compliance relative to daily SL BPN dosage forms, and may help prevent treatment noncompliance in higher-risk patients (i.e., those patients who take "drug holidays" from their BPN when they wish to abuse illicit opioids). In addition, CAM2038 q1w and q4w may provide significant potential for reducing risks of diversion, abuse, and accidental pediatric exposure, which continue to be important public health consequences of SL BPN therapy.

In addition an indirect health benefit to the patients enrolled in this trial is the free medical tests received during the study.

The available information suggests that the present clinical study has a favorable risk-benefit ratio.

6. STUDY OBJECTIVES

6.1. Primary Objective

The primary objective of the study is:

- To demonstrate the safety and tolerability of CAM2038 products in 12-month (48-week) BPN treatment in adult outpatients with opioid use disorder.

6.2. Secondary Objective

The secondary objective of the study is:

- To evaluate efficacy of CAM2038 through several efficacy parameters, including urine toxicology, signs and symptoms of withdrawal and cravings in adult outpatients with opioid use disorder.

7. INVESTIGATIONAL PLAN

7.1. Overall Study Design and Plan

This is an open-label multi-center, 12-month (48-week) safety study, consistent with standard practice for long-term safety studies. This one year safety study will utilize CAM2038 q1w (once weekly) and q4w (once monthly) and will have 3 phases: Screening, Treatment, and Follow-up.

Patients who are currently taking SL BPN (weekly or monthly prescription visits) or those individuals who are actively seeking BPN treatment but who have not yet begun a treatment regimen may be eligible for the study.

Following Screening, qualified subjects meeting inclusion criteria and not meeting exclusion criteria will be initiated on either CAM2038 q1w or q4w, based on their current treatment status (qualified subjects currently on SL BPN or seeking BPN treatment).

Qualified subjects will be initiated or transitioned to CAM2038 q1w or q4w as follows:

- Initiation of BPN treatment – initiate with CAM2038 q1w
- Currently on SL BPN treatments – transfer to corresponding CAM2038 q1w or q4w dose

Subjects will be allowed to receive temporary dose adjustments during the study with rescue booster SC injections of CAM2038 q1w 8 mg, at the discretion of the Investigator. Dose adjustments will also be allowed at scheduled visits.

During the Treatment Phase, subjects will receive CAM2038 treatment for up to 48 weeks. The study will end when at least 100 subjects have been exposed to CAM2038 for 12 months (48 weeks). All subjects will be transitioned back to usual care and followed for an additional 4 weeks (up to Week 53).

[figure not shown]
To ensure adequate enrollment and address potential inconvenience to subjects, all subjects will receive appropriate compensation for time and travel expenses related to attendance at study visits. All costs of medications and counseling will also be covered.

Germany only: The subject management procedures in the study comply with the statutory requirements in the German Verordnung über das Verschreiben, die Abgabe und den Nachweis des Verbleibs von Betäubungsmitteln (Betäubungsmittel-Verschreibungsverordnung – BtMVV, last amended 15 July 2009) and the drug substitution processes comply with German Richtlinien der Bundesärztekammer zur Durchführung der substituionsgestützten Behandlung Opiatabhängiger (19 February 2010).

The overall study design is illustrated in [Figure 4](#).

Section 9 provides additional information on the baseline, safety, and efficacy assessments included in the study. Study endpoints are described in Section 9.6 and Section 9.7. Statistical analysis is described in Section 11.

Figure 4: Overview of Study Design

BPN=buprenorphine; SL=sublingual.

Note: Subjects in the CAM2038 q1w once weekly group may be transferred to CAM2038 q4w once monthly at any time during the study at the Investigator's discretion, using the guidance provided in Section 7.1.2.3.

7.1.1. Screening Visit (Week -3 to Week -1):

Medical and eligibility screening will occur within 1-3 weeks of the Treatment Phase (Day 1). At Screening, subjects will provide written informed consent to participate in the study before any protocol-specified procedures or assessments are completed. The Screening Visit will include standard medical screening procedures, complete medical/psychosocial history, urine toxicology and detailed substance use and treatment history, as outlined in [Table 3](#).

7.1.2. Treatment Phase (Week 1 to Week 48)

7.1.2.1. Day 1 (Week 1) (CAM2038 q1w)

New entrants to BPN Treatment: On Day 1, for subjects who are **not currently receiving SL BPN or buprenorphine/naloxone (SL BPN/BPX)**, treatment will be initiated with CAM2038 q1w in the following manner:

Day 1: On Day 1, subjects will receive the following, while on site:

- A 4 mg SL BPN tablet test dose and observed for at least 1 hour prior to study drug administration.
- Once tolerability is confirmed (i.e., no precipitated withdrawal symptoms), a single CAM2038 q1w (once-weekly) 16 mg injection (0.32 mL of active) will be administered.

Day 2: All subjects will return to the clinic on Day 2 to ensure tolerability.

Day 4: All subjects will return to the clinic. Subjects who return on Day 4 still experiencing withdrawal symptoms should receive a single CAM2038 q1w 8 mg SC injection (0.16 mL of active). A visit window of

±1 day is allowed for the Day 4 visit.

Days 5 to 7: Subjects requiring additional dosage adjustments may return to the clinic on Days 5 to 7 if needed, based on withdrawal symptoms or tolerability. Subjects who require additional increases in dose will receive up to two additional CAM2038 q1w 8 mg SC injections (0.16 mL of active) (i.e., up to a maximum of 40 mg SC injection dose per week).

Subjects Currently on Weekly BPN Treatment: Subjects who are **currently receiving SL BPN/BPX** and are considered a candidate for CAM2038 q1w treatment by the Investigator will be transitioned to CAM2038 q1w in the following manner:

- Subjects will receive a single CAM2038 q1w SC injection that corresponds to their current SL BPN/BPX dose prior to Day 1:
 - ≤ 6 mg SL BPN/BPX: 8 mg (0.16 mL) CAM2038 q1w SC injection
 - 8-10 mg SL BPN/BPX: 16 mg (0.32 mL) CAM2038 q1w SC injection
 - 12-16 mg SL BPN/BPX: 24 mg (0.48 mL) CAM2038 q1w SC injection
 - 18-24 mg SL BPN/BPX: 32 mg (0.64 mL) CAM2038 q1w SC injection

- Subjects may return to the clinic for additional titration with CAM2038 q1w (8 mg SC booster injections), as needed, up to a maximum weekly dose of 40 mg per week.

Subjects should not take their ordinary SL BPN tablet(s) on Day 1 (i.e., the last dose of SL BPN should be taken on the day before dosing with CAM2038 q1w).

Subjects will return to the clinic for weekly visits during which they will receive their CAM2038 q1w SC injection treatments.

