7.5. Exclusion Criteria

Subjects will not be eligible to participate in this study if any one of the following exclusion criteria is met:

1. Current diagnosis of Acquired Immune Deficiency Syndrome (AIDS).
2. Current diagnosis of chronic pain requiring opioids for treatment.
3. Current DSM-V diagnosis for moderate to severe substance use disorder (including alcohol) other than opioids, caffeine or nicotine and currently being treated as the primary substance use disorder.
4. Recent history of or current evidence of suicidal ideation or active suicidal behavior as based on the Columbia Suicide Severity Rating Scale (C-SSRS) ("Yes" responses to questions 4 or 5).
5. Pregnant or lactating or planning to become pregnant during the study.
6. Hypersensitivity or allergy to naloxone (only for subjects receiving the SL BPX test dose), BPN or excipients of CAM2038.
7. Requires chronic use of agents that are strong inhibitors or inducers of cytochrome P450 3A4 (CYP 3A4) such as some azole antifungals (e.g., ketoconazole), macrolide antibiotics (e.g., clarithromycin), or protease inhibitors (e.g., ritonavir, indinavir, and saquinavir).
8. Hepatitis, unless under stable treatment, at the discretion of the Investigator.
9. Any pending legal action that could prohibit participation or compliance in the study.
10. Exposure to any investigational drug within the 4 weeks prior to Screening.
11. Aspartate aminotransferase (AST) levels ≥ 3 X the upper limit of normal, alanine aminotransferase (ALT), levels ≥ 3 X the upper limit of normal, total bilirubin ≥ 1.5 X the upper limit of normal, or creatinine ≥ 1.5 X upper limit of normal on the Screening laboratory assessments, or other clinically significant laboratory abnormalities, which in the opinion of the Investigator may prevent the subject from safely participating in study.
12. Participants with a history of risk factors of Torsades de Pointes (e.g., heart failure, hypokalemia, family history of Long QT Syndrome) or an ECG demonstrating a Fridericia's corrected QT interval (QTcF) >450 msec in males and QTcF > 470 in females at screening.

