8. TREATMENTS

8.1. Treatment Administration

Subjects will receive CAM2038 treatment for up to 12 months (48 weeks) during the study:

- For subjects who are not currently receiving SL BPN or SL BPN/BPX, treatment will be initiated with a single CAM2038 q1w 16 mg SC injection (following a 4 mg SL BPX test dose); additional dose adjustments will be allowed up to maximum weekly dose of 40 mg.
- Subjects who are currently receiving SL BPN/BPX will be transitioned to CAM2038 q1w or q4w SC injections according to their current dose of SL BPN/BPX (Table 2).
- SC injection administration sites: Rotate from left and right side of buttock. Injection with CAM2038 q1w will be rotated in a manner to not re-inject in the same location for at least 8 weeks, (i.e., injection into the same site will only occur after 8 weeks). Injection with CAM2038 q4w will be rotated and the same site will not be utilized for the duration of the study.
- Additionally, a q4w injection dose can be injected into a previously used q1w injection site following the q1w rule: Injection with CAM2038 q1w will be rotated in a manner to not re-inject in the same location for at least 8 weeks, (i.e., injection into the same site will only occur after 8 weeks)

A diagram of potential injection sites will be provided in the Study Manual of Procedures (MOP).

Table 2: Doses of CAM2038 q1w and q4w for Subjects Transitioning from SL BPN/BPX

Weekly SL BPN/BPX Category	Once Weekly CAM2038 q1w SC Injection^a
≤ 6 mg	8 mg (0.16 mL)
8-10 mg	16 mg (0.32 mL)
12-16 mg	24 mg (0.48 mL)
18-24 mg	32 mg (0.64 mL)
Monthly SL BPN Category	Once Monthly CAM2038 q4w SC Injection^b
8-10 mg	64 mg (0.18 mL)
12-16 mg	96 mg (0.27 mL)
18-24 mg	128 mg (0.36 mL)

26-32 mg	160 mg (0.45 mL)
----------	------------------

BPN = buprenorphine; BPX = buprenorphine/naloxone; SC = subcutaneous; SL = sublingual

^a Subjects may return to the clinic for additional dose adjustments with CAM2038 q1w at scheduled visits or 8 mg SC booster injections at unscheduled visits, as needed, up to a maximum weekly dose of 40 mg per week.

^b Subjects needing additional temporary BPN while receiving CAM2038 q4w may receive a maximum of two boosters of CAM2038 q1w 8 mg SC injection per week (i.e., unscheduled visits). Dose adjustments may also be implemented at the discretion of the Investigator at scheduled visits.

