8.2.3. Sublingual Buprenorphine/Naloxone

Subjects who are not currently receiving SL BPN or SL BPN/BPX at the time of study entry will receive a 4 mg test dose of BPX on Day 1. The BPX test dose consists of 2 SL tablets of Suboxone[®], each containing 2 mg BPN and 0.5 mg naloxone (Indivior UK Limited). Suboxone will be sourced locally, handling and storage of the product will be in accordance with the Suboxone Summary of Product Characteristics.

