2.0 LIST OF ABBREVIATIONS

| Abbreviation | Definition |
|--------------|---|
| AE | Adverse Event |
| BPN | Buprenorphine or Buprenorphine/Naloxone |
| COWS | Clinical Opiate Withdrawal Scale |
| CRF | Case Report Form (may include electronic data capture systems or paper forms) |
| C-SSRS | Columbia-Suicide Severity Rating Scale |
| ECG | Electrocardiogram |
| MedDRA | Medical Dictionary for Regulatory Activities |
| mg | Milligram |
| PT | MedDRA Preferred Term |
| SAE | Serious Adverse Event |
| SAP | Statistical Analysis Plan |
| SC | Subcutaneous |
| SD | Standard Deviation |
| SL | Sublingual |
| SOC | MedDRA System Organ Class |
| SOWS | Subjective Opiate Withdrawal Scale |
| TEAE | Treatment-Emergent Adverse Event |
| VAS | Visual Analogue Scale |
| WPAI-GH | Work Productivity and Activity Impairment Questionnaire General Health |

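### The Day 1 test dose for new entrants is SL buprenorphine in Protocol 7.1.2.1 but buprenorphine/naloxone in 8.1 and 8.2.3; the sections, and exclusion criterion 6, must be reconciled

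*Protocol*

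**What the plan says.** Three sections of the protocol describe the test dose given on Day 1 to subjects not already on sublingual treatment.

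- Section 7.1.2.1, the Day 1 procedure, lists "A 4 mg SL BPN tablet test dose and observed for at least 1 hour prior to study drug administration". Naloxone is not mentioned. The first CAM2038 q1w injection follows once tolerability is confirmed.
- Section 8.1, on treatment administration, has the first injection given "following a 4 mg SL BPX test dose".
- Section 8.2.3, devoted to the sublingual product, says these subjects "will receive a 4 mg test dose of BPX on Day 1". It specifies two Suboxone tablets, "each containing 2 mg BPN and 0.5 mg naloxone", sourced locally.

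The note to Table 2 defines the terms: "BPN = buprenorphine; BPX = buprenorphine/naloxone; SC = subcutaneous; SL = sublingual". The abbreviation list in Section 4 agrees.

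Exclusion criterion 6 in Section 7.5 depends on the test-dose product: "Hypersensitivity or allergy to naloxone (only for subjects receiving the SL BPX test dose), BPN or excipients of CAM2038".

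**The concern.** Section 7.1.2.1 is where site staff would look for the Day 1 steps. Read with the protocol's own definitions, it calls for a different product from the one in 8.1 and 8.2.3. Two things are at stake.

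The first is eligibility. Because criterion 6 applies naloxone hypersensitivity only where the BPX test dose is given, the answer to who is excluded depends on which section a site follows.

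The second is uniformity. The test dose decides whether the first injection goes ahead, and safety is the primary objective. The SAP (Section 8.2) lists Europe, the US and Australia as regions, and the named test product is obtained locally. Sites that read the text differently could give different products before the same injection.

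**Working it through.** No sample size, power or event count is involved, so the check is a comparison of the texts plus two multiplications.

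**Step 1: the amounts**

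From the tablet composition in Section 8.2.3:
- buprenorphine: 2 tablets × 2 mg = 4 mg, which matches the 4 mg in 7.1.2.1 and 8.1;
- naloxone: 2 tablets × 0.5 mg = 1 mg, where 7.1.2.1 mentions none.

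**Step 2: the sections side by side**

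| Feature | 7.1.2.1 | 8.1 | 8.2.3 |
|---|---|---|---|
| Buprenorphine | 4 mg | 4 mg | 4 mg |
| Product term | SL BPN | SL BPX | BPX (Suboxone) |
| Naloxone | not mentioned | implied by BPX | 1 mg |
| Presentation | 4 mg tablet dose, no count or strength | not stated | two tablets of 2 mg |

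The sections agree on the buprenorphine amount and disagree on the product. The difference in presentation is the weaker part: the word tablet in 7.1.2.1 may only describe the kind of dose and need not mean a single 4 mg tablet.

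**Step 3: can BPN in 7.1.2.1 be read as BPX?**

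The definitions keep the two apart. So does the sentence that introduces the disputed step, which describes new entrants as those "not currently receiving SL BPN or buprenorphine/naloxone (SL BPN/BPX". Section 5.3 also links SL BPN to Subutex, a different brand from the one in 8.2.3. A site that takes the term literally therefore has support in the text.

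**Step 4: what follows for a new entrant with naloxone hypersensitivity**

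| Site screens as if the test dose were | Site gives | Excluded under criterion 6 on naloxone grounds? | Naloxone given? |
|---|---|---|---|
| BPN (7.1.2.1) | BPN | No | No |
| BPX (8.1, 8.2.3) | BPX | Yes | No |
| BPX | BPN | Yes | No |
| BPN | BPX | No | Yes, 1 mg |

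Only the last row exposes the subject. It requires one reading at screening and the other at dosing.

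**Step 5: is the product given recorded?**

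The Schedule of Assessments (Table 3) has no row for the test dose, and SAP Appendix A has a listing for CAM2038 injections but none titled for the test dose. Against that, Section 8.2.1 requires detailed accountability for study drugs, and Section 8.7 requires all non-study medication to be documented. The CRF and the Manual of Procedures are not among the documents. Whether the product would be identifiable cannot be settled either way.

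**Step 6: do the planned analyses change?**

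SAP 11.1.2 defines treatment emergence by date. The test dose and the first injection both fall on Day 1, so the definition classifies an event the same way whichever product was used. SAP 6.1 sets baseline by the first CAM2038 dose. The sample size in Section 11.4 does not use the test dose.

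**The case against.** The strongest reply is that this is one loosely worded bullet. The protocol does not hold to its own abbreviations. Sections 7.1.2.1 and 7.1.2.2 tell subjects on either sublingual product to skip their usual SL BPN tablets. Inclusion criterion 6b names only SL BPN, although the dosing sections provide for BPX users. The SAP defines BPN as "Buprenorphine or Buprenorphine/Naloxone". Section 8.2.3 is the only place that gives a test product's brand, strength and source. Section 8.1 and criterion 6 match it, and Section 8.7 also refers to SL BPX during treatment. No section describes a buprenorphine-only test tablet any further. Most of this stands: 7.1.2.1 is the outlier and may be shorthand. It does not remove the conflict, because sites dose from the protocol, where the terms are defined as different.

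A second reply is that the qualifier in criterion 6 has an ordinary purpose. Transitioning subjects get no test dose, so it may simply separate them from new entrants. That is plausible, and its wording points a careful reader to BPX. It works only if the test dose is BPX, which is what 7.1.2.1 does not say.

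A third reply concerns safety. A reader might infer that the contradiction by itself puts hypersensitive subjects at risk. It does not: under either reading applied consistently, no such subject receives naloxone. Section 9.2 also requires each criterion to be documented before Day 1. This reply stands, and it reduces the risk to the mixed case.

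**Conclusion.** The protocol contradicts itself on the Day 1 test dose for new entrants. The buprenorphine amount agrees at 4 mg; the product does not, nor does the tablet presentation as written. This is an inconsistency in the dosing procedure, not a design choice, and it is worth correcting.

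The consequences are conditional. Exposure of a hypersensitive subject to 1 mg naloxone needs a site to screen by 7.1.2.1 and dose by 8.2.3. Use of different products across sites needs some sites to take 7.1.2.1 literally. The documents do not show that either happened. The disputed text covers all new entrants, but only those at sites following 7.1.2.1 literally would be handled differently. How many of the approximately 228 planned subjects are new entrants is not stated.

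A reader might also infer that Day 1 tolerability and adverse-event data would mix two products with nothing to tell them apart. The documents do not support that: mixed use is only a possibility, and without the CRF and the Manual of Procedures the absence of a record cannot be shown. No effect on sample size or planned analyses is shown.

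The conclusion rests on the protocol's definitions governing its own text, and on no document outside the two supplied resolving the conflict.

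**What to change.** - Reconcile Sections 7.1.2.1, 8.1 and 8.2.3 so that all name the same product and the same tablet presentation. Which product is right is for the sponsor to state.
- Align exclusion criterion 6 with that statement, so that screening and dosing rest on the same text.
- Confirm that the product given is recorded for each new entrant. If it is not, add it to the CRF.
- If subjects have already been dosed, check site records for the product used, so that any mixed use can be identified.

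The cost is a wording correction through the amendment route in Section 12.6 and at most one recorded item. No analysis changes.
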